**Figure 1 Study Design**

Note: CED: cohort entry date; RTI: respiratory tract infection; SOC: standard of care

-  For the patients who initiate OM-85 during the initiation grace period, another index date is assigned at the date of the 1st OM-85 prescription: OM-85 initiation date. This date is used as the index date in analyses on exclusively OM-85 initiators.
-  Outcomes defined for each objective are listed in [Table 7](#) and [Table 8](#).
-  Pregnancy at CED is estimated using a variable assessment window expanding from 183 days (6 months) before CED to 280 days (9 months) after CED, as detailed in [Section 3.2.2.3](#).
-  Selected covariates are defined during initiation grace period, to be used in sensitivity analysis for clone censor weighting.

period (see [Section 3.3.3](#)).

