### 3.2.2 Study Population

The overall study population will include patients  $\geq 1$  year of age with  $\geq 1$  RTI episodes and no prescriptions of bacterial lysates within 12 months prior to inclusion to the study. Additionally, included patients will be required to have  $\geq 12$  months of continuous enrolment in the database prior to inclusion. The inclusion criteria are detailed in [Table 4, Section 3.2.2.1](#). No exclusion criteria are applied for this study.

The CED is the date of the 2nd, 3rd, ... or nth RTI episode, i.e., the date of fulfilling this inclusion criterion. During the inclusion period, patients can have several CEDs. For patients with several CEDs, the CED of the patient used in the study will be selected randomly, which is one of the unbiased methods to select the date (29). Thus, each patient can enter the study only once.

Patients in the overall study population will be categorised to one of the two exposure groups (treatment strategies): patients who initiated OM-85 at the CED or during the 30-day initiation grace period, and SOC/non-user group of patients who did not initiate OM-85 at the CED or during the 30-day initiation grace period.

The primary and secondary objectives and the exploratory objectives **CCI** will be studied in the overall study population ([Table 3](#)). The exploratory objectives **CCI** **CCI** **CCI**. The sub-populations applied in this study are further described in [Section 3.2.2.3](#).

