**Table 3 Populations for Each Study Objective**

Objective		Population In Which Studied and Index Date
Primary objectives		
1	RTI rate 12 months before and 12 and 24 months after initiating OM-85	
 
OM-85 initiators only, within the overall study population
 
Index date: OM-85 initiation date
 

2	Comparative effectiveness – rate of RTI episodes during follow-up at 12 and 24 months	
 
Both exposure groups (OM-85 initiators and SOC/non-user group) within the overall study population
 
Index date: end of initiation grace period
 

Secondary objectives		
1	Patient characteristics at CED	
 
Both exposure groups (OM-85 initiators and SOC/non-user group) within the overall study population
 
Index date: CED
 

2	Descriptive pattern of prescribing OM-85	
 
OM-85 initiators only, within overall study population
 
Index date: OM-85 initiation date
 

3	RTI rate 12 months before and 6 and 9 months after initiating OM-85	
 
OM-85 initiators only, within the overall study population
 

Objective		Population In Which Studied and Index Date
		
 
Index date: OM-85 initiation date
 

4	Comparative effectiveness – rate of RTI episodes during follow-up at 6 and 9 months	
 
Both exposure groups (OM-85 initiators and SOC/non-user group) within the overall study population
 
Index date: end of initiation grace period
 

5	Descriptive pattern of prescribing antibiotics during follow-up	
 
Both exposure groups (OM-85 initiators and SOC/non-user group) within the overall study population
 
Index date: end of initiation grace period
 

6	Descriptive pattern of concomitant medications of interest during follow-up	
 
Both exposure groups (OM-85 initiators and SOC/non-user group) within the overall study population
 
Index date: end of initiation grace period
 

7	Descriptive healthcare resource utilisation during follow-up	
 
Both exposure groups (OM-85 initiators and SOC/non-user group) within the overall study population
 
Index date: end of initiation grace period
 

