### 3.3.1.2 Pattern of Prescribing OM-85 (Secondary Objective 2)

For the OM-85 group, the following will be defined to analyse treatment patterns:

- **OM-85 initiation date:** The OM-85 initiation date will be the date of the first observed prescription of OM-85 at CED or during the 30-day initiation grace period.
- **OM-85 renewal date:** The prescription date for each subsequent OM-85 prescription during the follow-up is an OM-85 renewal date.
- **Prescribed quantity:** Prescribed quantity is defined as the number of units (capsules or sachets) prescribed to the patient at OM-85 initiation and renewal dates.
- **Daily dose:** The dose is assumed to be 1 unit, i.e. capsule or sachet, per day (24), unless if a specific other daily dose is directly available in the database.
- **Prescribed dose:** The strength of the prescribed units, 7 mg or 3.5 mg, is considered the prescribed dose, unless if a specific other prescribed dose is directly available in the database.
- **Prescription duration:** The duration of each prescription is equal to the prescribed quantity (assuming the one unit per day), multiplied by 3 because OM-85 is prescribed in 10-day courses per month). For example, if a patient is prescribed 10 capsules, the duration of the prescription is 30 days. The start of the prescription duration is the OM-85 initiation or the renewed OM-85 prescription's start date (see definition below).
  - **Cumulative prescription duration of overlapping prescriptions:** If the OM-85 renewal date occurs before the previous prescription duration has ended (or at the end date), the durations of both (or more) prescription durations will be summed. For example, if the prescription duration of the first OM-85 prescription at OM-85 initiation date is 30 days (based on 10 prescribed units) and the patient receives another 30-day prescription 20 days after the OM-85 initiation date, the cumulative prescription duration is 60 days from OM-85 initiation date.

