**Main RTI episode definition**

CCI [redacted]  
CCI [redacted]

CCI [redacted]  
CCI [redacted]  
CCI [redacted]

CCI [redacted]  
CCI [redacted]

Hence, with this definition, 14 days is the maximum length of an RTI episode. Sensitivity analyses may be performed with altered maximum length: 7 days and 21 days.

CCI [redacted]  
CCI [redacted]  
CCI [redacted]  
CCI [redacted]  
CCI [redacted]  
CCI [redacted]  
CCI [redacted]  
CCI [redacted]

CCI [redacted]

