Secondary objective 2: Prescribing OM-85	Pattern of prescribing of OM-85	
 
Number of prescriptions of OM-85
 
Prescribed dose
 
OM-85 cycle duration in days
 
Number of and interval time between treatment cycles
 
	
 
The variables needed for treatment patterns are defined in Section 3.3.1.2
 
Continuous variables (number of prescriptions, prescribed dose, OM-85 cycle duration in days, number of and interval time between treatment cycles)
 
Categorical variables, e.g., OM-85 cycle duration < 90 days; 90 days, > 90 days to <math>\leq 180</math> days, or > 180 days; <math>\geq 2</math> treatment cycles
 
At OM-85 initiation date and thereafter during follow-up at 3, 6, 9, 12, and 24 months
 

Objective	Outcome	Definition	Measurement
Secondary objectives 3-4: Rates of RTI episodes	RTI episode	
 
The episode start date is defined as the date of the first observed diagnosis, and the end date is defined as when a different diagnosis code is available, or after 14 days of the first diagnosis
 
Record of ICD-9/ICD-10 of URTI, LRTI, Other RTIs (Appendix 3)
 
	
 
Rate of RTI episodes at 12-month baseline and during follow-up at 3, 6, 9, 12, and 24 months
 
Rate variable
 

Secondary objective 5: Prescribing antibiotics	Pattern of prescribing of antibiotics	
 
Penicillin/beta-lactams, macrolides, cephalosporins, doxycycline, others, defined using country-specific codes (ATC, AIC, Other) (Appendix 4)
 
	
 
Binary variable (Yes/No for each class of medication prescribed)
 
Continuous variable (number of prescriptions, length of treatment in days)
 
At 12-month baseline and during follow-up at 3, 6, 9, 12, and 24 months
 

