### 3.9.4 Time-Related Biases

Time-related biases were minimised by designing the study using the TTE framework (28,29). Importantly, follow-up was carefully selected to start at the end of the initiation grace period, equally for both exposure groups to eliminate immortal time bias. Starting follow-up at OM-85 initiation date for the OM-85 groups, and at CED for the SOC/non-user group would inevitably result in immortal time bias.

The initiation grace period was defined as 30 days, based on alignment with clinicians on a reasonable time for prescribers to prescribe preventive treatment with OM-85 after an RTI. Alternative grace periods may be considered in the SAP.

The time windows to detect the outcomes during the follow-up were chosen based on evidence from interventional studies on OM-85 with up to 12-month follow-up (24). In this study in real-world settings, follow-up was extended to 24 months, with the opportunity to investigate longer-term effectiveness and thereby complement the results of interventional studies. No bias is anticipated from this maximum 24-month window to detect outcomes.

The OM-85 treatment strategy was considered static (Section 3.3.1), based on its clinical use. However, in the static treatment strategy in the main analysis, OM-85 initiators will not be censored if/when they are prescribed other bacterial lysates during the follow-up. While this is consistent with the chosen treatment strategy, the time window for detecting the outcomes associated with OM-85 is not free from the effect of other bacterial lysates. Therefore, censoring follow-up at the first date of a prescription of another bacterial lysate will be applied in a sensitivity analysis, for both exposure groups.

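### The before-after analyses can open the post-initiation window inside the still-open CED episode, and the protocol gives conflicting start dates; the effect is of unknown sign and matters mainly at 3 months

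*Protocol*

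**What the plan says.** The clock for the before-after objectives comes from three places in the protocol. Table 3 gives, for primary objective 1 and secondary objective 3, "Index date: OM-85 initiation date". Figure 1 note 1 says of the first prescription date: "This date is used as the index date in analyses on exclusively OM-85 initiators". Section 3.3.1.2 supplies the definition: "The OM-85 initiation date will be the date of the first observed prescription of OM-85 at CED or during the 30-day initiation grace period". Hence the window can open on any day from 0 to 30 after the CED.

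Other places give a different clock. The synopsis (Overall Design and Follow-up period) assesses outcomes after the grace period and starts follow-up at its end for each included patient, without limiting this to the two-group comparison. Section 3.1 assesses outcomes from the CED. Section 3.2.1 limits the day-30 start to the comparative effectiveness analysis.

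Section 3.2.2 makes the CED the date of the patient's second or later RTI episode. On episode length, Section 3.3.2.1 says that "14 days is the maximum length of an RTI episode". Table 8, in the row for secondary objectives 3-4, says that "the end date is defined as when a different diagnosis code is available, or after 14 days of the first diagnosis". Much of the main episode definition in Section 3.3.2.1 is redacted.

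**The concern.** A prescription on days 0-13 can fall while the CED episode is still open. Under the visible Table 8 rule, two things can then happen that have nothing to do with the drug.

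- **Blocking.** A further record of the same code belongs to the CED episode, so no new episode can start until the 14 days are over. If those days still count as person-time, the early post-initiation rate is too low. The pre-initiation window does not systematically begin inside an open episode.
- **Adding.** A different code recorded after the prescription closes the CED episode, and the same illness can be counted as a new RTI after OM-85. The early rate is then too high.

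Both effects are concentrated in the first two weeks, so they weigh most in the 3-month window and fade in longer ones. At stake is whether the time pattern across 3, 6, 9, 12 and 24 months reflects OM-85 or the coding of the index illness. Section 3.1.1 calls the objectives outside the comparative set free of time-related bias. The before-after limitations in Section 3.9.1.1 do not mention an open index episode. The 7-day and 21-day sensitivity analyses in Section 3.7.7 leave the start date where it is, and clone-censor weighting covers primary objective 2 only.

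**Working it through.** **Inputs from the protocol.** Baseline rate 2 RTIs per person-year (Section 3.5); maximum episode length d = 14 days (Section 3.3.2.1), 21 days in a sensitivity analysis (Section 3.7.7); prescription on day s = 0 to 30 after the CED; windows W of 91, 183, 274, 365 and 730 days.

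**Assumptions.** No drug effect, so the true ratio is 1.00. All days in the window count as time at risk. The CED episode itself is counted in neither window. The distribution of s and the share re-coded are not in the protocol and are varied.

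**The plan's own figure.** The protocol gives no figure for this point. Its precision table for the before-after IRR (Table 9) was recomputed from the stated F-quantile interval: all 32 cells agree to three decimals, including 0.197 at 350 person-years and IRR 0.9. The table is correct, but it addresses precision, not this bias.

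**Step 1, blocking alone.** The approximate ratio is 1 − (mean blocked days)/W.

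- All prescribed on the CED: 14 blocked days. At 3 months 1 − 14/91 = 0.846; at 12 months 1 − 14/365 = 0.962; at 24 months 1 − 14/730 = 0.981.
- All prescribed on day 7: 7 blocked days. At 3 months 1 − 7/91 = 0.923.
- Starts uniform over 30 days: mean blocked days 14²/(2 × 30) = 3.27. At 3 months 1 − 3.27/91 = 0.964; at 12 months 1 − 3.27/365 = 0.991.

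Simulation gives nearly the same values. They are slightly higher because a patient is certain to be free of an episode just after the block ends.

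| Prescription day | 3 mo | 6 mo | 9 mo | 12 mo | 24 mo |
|---|---|---|---|---|---|
| All on the CED | 0.85 | 0.93 | 0.95 | 0.96 | 0.98 |
| All on day 7 | 0.93 | 0.97 | 0.98 | 0.98 | 0.99 |

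Spread starts gave 0.96-0.97 at 3 months. With the 21-day cap, same-day starts give about 0.78 at 3 months. At 1 or 3 RTIs per year the ratios hardly change.

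**Step 2, adding alone.** If a share p of initiators has one extra counted episode, the ratio is 1 + p/(2 × W/365.25). At 3 months the expected count is 2 × 91/365.25 = 0.498, so p = 5% gives 1.10 and p = 10% gives 1.20. At 12 months p = 10% gives 1.05.

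**Step 3, both together.** Here 5-10% of all illnesses, before and after initiation, are re-coded on a random day within the 14 days. At 3 months the net ratio is about 0.95-1.04 for same-day starts and 0.98-1.01 for spread starts. At 12 months it is about 0.99-1.01 even for same-day starts.

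**Step 4, moving the clock.** When counting starts only once the CED episode has closed, the ratio returns to about 1.00 in every window. This was run with a 7-day episode and a start on day 7.

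**The case against.** The strongest case against has four parts.

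- **Hidden rules.** Most of the main episode definition is redacted, and Table 8 gives only a short form. A rule for episodes that straddle the index date may exist. Section 3.7.3 uses time at risk as the offset; if days inside an open episode are excluded from it, blocking largely disappears, though adding does not. This stands, and it is why the point is conditional on the visible rule.
- **Unusual scenario.** The 0.85 needs everyone to be prescribed on the CED. Section 3.2.1 calls same-day prescribing unrealistic to expect, and Section 3.1.1 says that requiring it would leave very few OM-85 patients. This stands: 0.85 is a bound, not an expected value.
- **Opposite signs.** The two effects partly cancel, as Step 3 shows. This also stands.
- **Cost of a day-30 start.** The objectives ask about rates after initiation, and a day-30 start would discard genuine post-prescription time. This is a fair reason against making day 30 the main rule.

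A reader might infer that an inert drug would show a strong early benefit that wanes, or that everyone treated in the first 14 days is affected. The document supports neither. The sign is not determined, and a different code recorded before the prescription already closes the CED episode under Table 8. Nor does the statement in Section 3.9.4 that "follow-up was carefully selected to start at the end of the initiation grace period, equally for both exposure groups to eliminate immortal time bias" contradict the before-after clock, since it concerns the comparison of the two exposure groups.

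**Conclusion.** The defect is real but modest. Table 3 and Figure 1 note 1 let the post-initiation window open inside the index illness, the visible rules do not say what happens then, and the synopsis and Section 3.1 give other start dates. On the stated assumptions the 3-month before-after ratio under no effect lies at about 0.98-1.01 for starts spread over the grace period and 0.95-1.04 for same-day starts once 5-10% re-coding is allowed; with blocking alone the bound is 0.85. For scale, Section 3.5 calls an IRR of 0.9 a small effect. At 12 and 24 months blocking moves the ratio by at most about 3-4% and 2%, so primary objective 1 is little affected. The exposure is mainly secondary objective 3 at 3 months. Net direction and size cannot be fixed from the protocol, because neither the share prescribed within 14 days nor the share re-coded is given, and part of the episode definition is redacted.

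**What to change.** First, reconcile the synopsis (Overall Design, Follow-up period) and Section 3.1 with Figure 1 note 1, Section 3.2.1 and Table 3, so that one start date holds for the before-after analyses.

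Second, for primary objective 1 and secondary objective 3, open both the RTI count and its person-time at the later of OM-85 initiation and CED + 14 days (CED + 21 days in the 21-day sensitivity analysis). State that RTI codes before that date belong to the CED episode and to neither window. A start at day 30, matching primary objective 2, can be a sensitivity analysis.

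The cost is a sentence in the protocol or SAP and one date in the program. The downside is that up to 14 days after the prescription (21 in that sensitivity analysis) are not counted for early starters.

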## 3.3.2 Outcomes

### 3.3.2.1 Primary Outcome

The primary outcome is the rate of RTI episodes.

The below definitions of RTI episodes are based on ICD-9/ICD-10 diagnosis codes (as defined in [Appendix 3 in Section 8.3](#)) and are sub-categorised as Upper, Lower RTI or Other RTIs-related diagnoses, and Other diagnoses.

**Main RTI episode definition**

CCI [redacted]  
CCI [redacted]

CCI [redacted]  
CCI [redacted]  
CCI [redacted]

CCI [redacted]  
CCI [redacted]

Hence, with this definition, 14 days is the maximum length of an RTI episode. Sensitivity analyses may be performed with altered maximum length: 7 days and 21 days.

CCI [redacted]  
CCI [redacted]  
CCI [redacted]  
CCI [redacted]  
CCI [redacted]  
CCI [redacted]  
CCI [redacted]  
CCI [redacted]

CCI [redacted]

**Alternative definitions**

Alternative RTI outcome definitions will be explored in Step 1 of the analysis using baseline data ([Section 3.7.8](#)). Two alternative definitions are utilised:

***Alternative 1 – Simple RTI diagnosis code***

An RTI episode is comprised of one RTI-related diagnosis. With this definition, each ICD-9/ICD-10 code for an Upper or Lower RTI will be counted as an RTI episode, regardless of the time elapsed between two codes.

### 3.3.2.2 Secondary and Exploratory Outcomes

The secondary and exploratory outcomes are described in [Table 8](#).

**Table 8 Secondary and Exploratory Outcomes**

Objective	Outcome	Definition	Measurement
Secondary objective 1  : Baseline characteristics	Sex	
 
Biological sex
 
	
 
Dichotomous variable (male/female)
 
Measurement at CED
 

	Age	
 
Age at index date
 
	
 
Categorical variable (1 to < 6 years, ≥ 6 to < 12 years, ≥ 12 to < 18 years, ≥ 18 to < 65 years and ≥ 65 years)
 
Measurement at CED
 

	BMI	
 
BMI = weight(kg)/height(m)
 
	
 
Continuous variable
 
Measurement closest to CED, during the 12-month baseline period
 

	Type and number of previous RTI episodes	
 
URTI only (e.g., acute nasopharyngitis, acute sinusitis, acute pharyngitis, acute tonsillitis)
 
LRTI only (e.g., whooping cough, pneumonia, acute bronchitis)
 
Other RTIs only: RTI not classified as upper or lower
 
Combination of URTI, LRTI, and/or Other RTIs
 
	
 
Categorical variable (diagnosis-related ICD-9/ICD-10 code, Appendix 3)
 
Continuous variable (number of URTIs, LRTIs, Other RTIs, URTI/LRTI/Other RTIs combined)
 
Measurement in the 12-month baseline period
 

	Comedications	
 
LABA, LAMA, ICS, LABA/ICS, LABA/LAMA, LABA/LAMA/ICS, antiallergic agents, leukotriene receptor antagonists, symptom relievers, systemic corticosteroids, systemic oral corticosteroids, influenza vaccines, influenza antivirals defined using country-specific drug codes (ATC, AIC, Other) (Appendix 4)
 
	
 
Binary variable (yes/no for each class of medication prescribed)
 
Continuous variable (number of prescriptions, length of treatment in days)
 
Measurement in the 12-month baseline period
 

	Antibiotic prescriptions	
 
Penicillin/beta-lactams, macrolides, cephalosporins, doxycycline, others, defined using country-specific codes (ATC, AIC, Other) (Appendix 4)
 
	
 
Binary variable (yes/no for each class of medication prescribed)
 
Continuous variable (number of prescriptions, length of treatment in days)
 
Measurement in the 12-month baseline period
 

	Comorbidities	
 
Smoking status and alcohol use, as recorded in the database
 
	
 
Binary variable (yes/no)
 

Objective	Outcome	Definition	Measurement
		
 
COPD (including CB), chronic lung disease, asthma, immunocompromised conditions, kidney diseases, liver diseases, cancer, malnutrition, food allergy, congenital malformations of the respiratory tract, ischaemic stroke, heart failure, atrial fibrillation, myocardial infarction, coronary heart disease, diabetes, gastro-oesophageal reflux, allergic rhinitis, atopic dermatitis, defined as <math>\geq 1</math> record of the ICD-9/ICD-10 codes (Appendix 3)
 
	
 
Measurement in the 12-month or the maximum baseline period. The maximum baseline period will be used for selected comorbidities that could have occurred earlier but may not be recorded in the data during the 12-month baseline period, such as allergies (allergic rhinitis and food allergy), myocardial infarction and cancer. These will be detailed in the SAP
 

	Overall and RTI-specific healthcare resource utilisation 	
 
Overall and RTI-specific visits, where RTI-specific visit is defined as a healthcare visit associated with an RTI diagnosis code
 
Type of healthcare visit: primary care / outpatient care visit, emergency care visit, hospital admission, ICU admission
 
Number of visits
 
Length of stay (for hospitalisation and ICU stays)
 
	
 
Continuous variable (number of visits, length of stay in days)
 
Measurement in the 12-month baseline period
 

Secondary objective 2: Prescribing OM-85	Pattern of prescribing of OM-85	
 
Number of prescriptions of OM-85
 
Prescribed dose
 
OM-85 cycle duration in days
 
Number of and interval time between treatment cycles
 
	
 
The variables needed for treatment patterns are defined in Section 3.3.1.2
 
Continuous variables (number of prescriptions, prescribed dose, OM-85 cycle duration in days, number of and interval time between treatment cycles)
 
Categorical variables, e.g., OM-85 cycle duration < 90 days; 90 days, > 90 days to <math>\leq 180</math> days, or > 180 days; <math>\geq 2</math> treatment cycles
 
At OM-85 initiation date and thereafter during follow-up at 3, 6, 9, 12, and 24 months
 

Objective	Outcome	Definition	Measurement
Secondary objectives 3-4: Rates of RTI episodes	RTI episode	
 
The episode start date is defined as the date of the first observed diagnosis, and the end date is defined as when a different diagnosis code is available, or after 14 days of the first diagnosis
 
Record of ICD-9/ICD-10 of URTI, LRTI, Other RTIs (Appendix 3)
 
	
 
Rate of RTI episodes at 12-month baseline and during follow-up at 3, 6, 9, 12, and 24 months
 
Rate variable
 

Secondary objective 5: Prescribing antibiotics	Pattern of prescribing of antibiotics	
 
Penicillin/beta-lactams, macrolides, cephalosporins, doxycycline, others, defined using country-specific codes (ATC, AIC, Other) (Appendix 4)
 
	
 
Binary variable (Yes/No for each class of medication prescribed)
 
Continuous variable (number of prescriptions, length of treatment in days)
 
At 12-month baseline and during follow-up at 3, 6, 9, 12, and 24 months
 

Secondary objective 6: Concomitant medications of interest	Pattern of concomitant medications of interest	
 
LABA, LAMA, ICS, LABA/ICS, LABA/LAMA, LABA/LAMA/ICS, anti-allergic agents, leukotriene receptor antagonists, symptom relievers, systemic corticosteroids, systemic oral corticosteroids, influenza vaccines, influenza antivirals
 
Defined using country-specific codes (ATC, AIC, Other) (Appendix 4)
 
	
 
Binary variable (Yes/No for each class of medication prescribed)
 
Continuous variable (number of prescriptions, length of treatment in days)
 
At 12-month baseline and during follow-up at 3, 6, 9, 12, and 24 months
 

Secondary objective 7  : Healthcare resource utilisation	Overall and RTI-specific healthcare resource utilisation	
 
Overall and RTI-specific visits, where RTI-specific visit is defined as a healthcare visit associated with an RTI diagnosis code
 
Type of healthcare visits: primary care / outpatient care visit, emergency care visit, hospital admission, ICU admission)
 
Number of visits
 
Length of stay (for hospitalisation and ICU stays)
 
	
 
Continuous variables (number of visits, length of stay in days)
 
During follow-up at 3, 6, 9, 12, and 24 months
 

Exploratory objectives CCI	CCI CCI CCI CCI	CCI CCI CCI CCI CCI CCI CCI CCI	
 
Exploratory objective CCI CCI CCI CCI CCI
 
Exploratory objective CCI CCI
 

Objective	Outcome	Definition	Measurement
			CCI [redacted] CCI [redacted]
Exploratory objective [redacted]	CCI [redacted] CCI [redacted] CCI [redacted] CCI [redacted] CCI [redacted] CCI [redacted] CCI [redacted]	CCI [redacted] CCI [redacted] CCI [redacted] CCI [redacted] CCI [redacted] CCI [redacted] CCI [redacted] CCI [redacted] CCI [redacted] CCI [redacted]	CCI [redacted] CCI [redacted] CCI [redacted] CCI [redacted] CCI [redacted]
Exploratory objectives [redacted]	CCI [redacted]	CCI [redacted] CCI [redacted] CCI [redacted] CCI [redacted] CCI [redacted] CCI [redacted] CCI [redacted] CCI [redacted] CCI [redacted] CCI [redacted] CCI [redacted] CCI [redacted]	CCI [redacted] CCI [redacted] CCI [redacted] CCI [redacted] CCI [redacted]
Exploratory objective [redacted]	CCI [redacted] CCI [redacted]	CCI [redacted] CCI [redacted] CCI [redacted] CCI [redacted] CCI [redacted] CCI [redacted] CCI [redacted]	CCI [redacted] CCI [redacted] CCI [redacted] CCI [redacted] CCI [redacted]
Exploratory [redacted]	CCI [redacted] CCI [redacted]	CCI [redacted] CCI [redacted] CCI [redacted] CCI [redacted] CCI [redacted] CCI [redacted]	CCI [redacted] CCI [redacted] CCI [redacted] CCI [redacted]
Exploratory objective [redacted]	CCI [redacted] CCI [redacted] CCI [redacted]	CCI [redacted] CCI [redacted] CCI [redacted] CCI [redacted] CCI [redacted]	CCI [redacted] CCI [redacted] CCI [redacted] CCI [redacted] CCI [redacted]
Exploratory objective [redacted]	CCI [redacted] CCI [redacted] CCI [redacted]	CCI [redacted] CCI [redacted] CCI [redacted] CCI [redacted] CCI [redacted]	CCI [redacted] CCI [redacted] CCI [redacted] CCI [redacted] CCI [redacted]

Objective	Outcome	Definition	Measurement
Exploratory objective CCI	CCI CCI CCI	CCI CCI CCI CCI	CCI CCI CCI CCI CCI CCI CCI
Exploratory objective CCI	CCI CCI CCI	CCI CCI CCI CCI	CCI CCI CCI CCI CCI CCI CCI

CCI

 THIN databases (Italy and Belgium) do not cover hospitalisation stays or visits to the ICU or emergency care, while the Inspur database (China) does not cover primary care.

Note: AIC: Autorizzazione all’Immissione in Commercio; ATC: Anatomical Therapeutic Chemical; BMI: body mass index; CB: chronic bronchitis; CED: cohort entry date; COPD: chronic obstructive pulmonary disease; ICD-9: International Statistical Classification of Diseases and Related Health Problems 9th Revision; ICD-10: International Statistical Classification of Diseases and Related Health Problems 10th Revision; ICS: inhaled corticosteroids; ICU: intensive care unit; LABA: long-acting beta agonist; LAMA: long-acting muscarinic antagonist; LRTI: lower respiratory tract infection; RTI: respiratory tract infection; SAP: statistical analysis plan; URTI: upper respiratory tract infection.

ICD-9 codes will be provided in the SAP.

